A checklist for high schools' development/revision of the alcohol policy was developed with the aim to limit availability of alcohol, help enforcement and communicate clear attitudes to alcohol. The checklist was based on evidence from the national alcohol policies [30, 31] that have shown effect previously and interviews with principals to ensure feasibility. Most initiatives were mandatory to implement; however, some initiatives were optional because of implementation challenges or weaker evidence of impact. Headmasters will receive the checklist and be asked to tick the initiatives they intend to introduce before the new 1st year high school students begin in August 2019. Each school can decide for itself whether they also want to introduce the optional items in the checklist. Headmasters are asked to sign the adapted checklist and return it to the Danish Cancer Society to be published on the project's website. In this way, the checklist can also become a tool for leaders to promote and label their high school as a responsible institution. Headmasters are responsible for implementing and enforcing the new policy.

School educational components

-Web based education for social student committees that organize events where alcohol is sold such as parties, cafés, concerts etc. were developed, alongside with an web-based educational program for the introduction committee welcoming 1st year high school students to the high school.

The purpose of the web-based educational programs to the social student committees and intro committees is to make students aware of their responsibility for developing inclusive events, were students that do not drink also feel welcome, and the fact that they act as role models for their peers. The programs will provide information on national legislation on alcohol at high schools, marketing of alcohol, school alcohol policy, information on drinking peer pressures and social norms for adolescent alcohol use. Further, the programs provide guidance to arrange appealing social events without focusing on alcohol.

Pocket movie campaign

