At the parents' meeting, the parents will receive an information leaflet on young people's alcohol consumption and attitudes, and what they can do to prevent excessive alcohol consumption among their children. The Information leaflet will also contain links to the website.

-Website for parents

The information website is designed to provide parents with information on how their attitudes toward alcohol are still important to how much their children drink and give parents the skills to discuss alcohol with their child and make agreements.

Figure 1: Program Theory of the High Schools- High on life intervention

Evaluation design**Effect evaluation**

Intervention effects will be evaluated in a cluster-randomized controlled trial. Based on power calculations, we plan to include a random sample of 16 high schools randomly 1:1 allocated to either intervention or control using stratified covariate-constrained randomization [38]. The randomization process will be stratified on whether the school was an independent general high school or the school is embedded within a broader youth educational institution, and furthermore school information on school size measured by number of students, proportion of parents with high educational level and degree of urbanization will be balanced using the CCR SAS macro [39]. All general high schools were invited to participate in The Danish National Youth Study 2019 (n=150), which served as the baseline for the evaluation of the *High schools High on life* intervention. 53 general high schools participated in The Danish National Youth Study 2019 (response rate: 35%) and were invited to participate in *High schools High on life*. 16 high schools agreed to participate (participation rate: 30%). Main reasons for declining participation was lack of resources or participation in other studies.

Intervention

Intervention high schools will be asked to introduce the intervention components.

Control high schools will be asked to continue business as usual in the intervention period (the school year 2019-2020) and offered the intervention afterwards (in the school year starting in 2020).

Inclusion criteria

- High schools were invited to participate in the study if they participated in the Danish National Youth Study 2019.
- General high schools

Exclusion criteria

- High schools that did not participate in the Danish National Youth Study 2019
- Non-general high school students.

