- Students younger than 15 years or older than 25 years of age.

Ethics

Behavioral health prevention interventions are generally not required to notify for etic approval by the Scientific Ethics Committees{Scientific Ethics Committee, 2019 #172}. A query has been sent to the Scientific Ethics Committees for the Capital Region of Denmark (19021957).

According to the Danish Ethic Scientific Committee Act, only health science research projects must be notified to a scientific ethics committee. "Health science research project" is a concept that is defined partly in the committee act itself and partly in the executive order on the law.

Section 2 (1) of the Committee Act has the following definition of a health science research project;

§ 2. For the purposes of this Act:

1) Health science research project: A project involving experiments on live-born human subjects, human germ cells, which are intended to be used for fertilization, human fertilized eggs, embryos and fetuses, tissues, cells and human, fetus, and hereditary components or deceased. This includes clinical trials on medicinal products in humans, cf. No. 2, and clinical testing of medical devices, cf.

Data collection

The student questionnaire is based on items from other studies (e.g. The HBSC Study and the Danish National Youth Study 2014) either transferred without any revision or adapted to the high school setting [40, 41]. A few items will be developed specifically to the *High Schools- High on life* program. The student baseline alcohol questionnaire was tested among 4 high school students (3 girls and 1 boy) and followed by an interview about comprehensiveness, layout etc. The questionnaire was modified according to the students' comments and suggestions. 1st year high school students' response of the Danish National Youth Study 2019 questionnaire will serve as the baseline for the effect evaluation. The Danish National Youth Study 2019 questionnaire took around 45 minutes to answer. All 1st year high school students in intervention and the control schools should answer the follow-up questionnaire. The follow-up questionnaires will only include questions relevant to the intervention and take around 15 minutes to answer. All student questionnaires will be electronic internet-based and answered in class. Baseline data was collected from January to March 2019, while follow-up data will be collected from March to April 2020.

Outcomes

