The primary outcome is mean number of binge drinking occasions within the last 30 days. 1st year high school students will be asked "*how many times within the last 30 days have you been drinking 5 or more units of alcohol within one occasion?*". Secondary outcomes are 1) mean weekly alcohol consumption, 2) mean alcohol intake at last school party, 3) mean alcohol intake at the school during

last school party, and 4) proportion of students who think alcohol plays a too dominant part at the school (see Table 1).

Explorative outcomes: a potential positive side effect of the intervention is that a higher proportion of students feels included in the social community at school. We want to look at this among all students and further do a stratified analysis among students who do not drink or have a low alcohol intake (25% lowest quantile in mean weekly alcohol consumption at baseline among students in both interventions and control group). A potential negative side effect of the intervention is a higher alcohol intake among students in the intervention group as a response to increased focus on alcohol, making it more interesting among students in intervention group. We will also study substitute effects by analyzing whether students in the intervention group are more likely to experiment with drugs as compared to students in the control group.

Table 1: Outcomes and mediators

Variable	Question	Type	Units/categories
Primary outcome			
Binge drinking occasions	How many times within the last 30 days have you been drinking 5 or more units of alcohol within one occasion?	Continuous	Occurrences
Secondary outcomes			
Weekly alcohol consumption	How many units of alcohol have you been drinking on each day during the last week?	Continuous	Units of alcohol
Alcohol intake at last school party	How many units of alcohol did you drink at the last high school party you attended?	Continuous	Units of alcohol
Alcohol intake at the school during last school party	How many units of alcohol did you drink at the school during high school party you attended?	Continuous	Units of alcohol
Proportion of 1 st year high school students who think alcohol play a too dominant part at the school	Do you feel that alcohol plays a too dominant part at your high school (e.g.	Binary	Yes/no

*at high school parties, school bars,
introduction trips, study tours etc.)?*

Explorative outcomes

Potential positive side effects

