A blinded version of the data will be used for data analysis. Outcomes will be analyzed after the principle of intention-to-treat including all students in the arm to which they were allocated independently of whether they received (or completed) the intervention as planned. Intention-to-treat analysis will be supplemented by per protocol analysis based on the implementation of intervention components (both on school and individual level). Multi-level models will be used to account for the clustering of students in schools and school classes. General and generalized linear models will be used to study continuous and binary outcomes. If the model assumptions of the general linear model are not fulfilled, transformation of the outcome will be performed. All analyses will be adjusted for sex, parental education level, parental income and baseline level of the outcome, to increase precision. Differential effects of intervention by sex, parental educational level on the primary outcome will be investigated (explorative analyses). We hypothesize that boys may experience stronger intervention effects than girls due to higher initial level of binge drinking [43]. We had no hypotheses of the direction of socioeconomic differences in intervention effects, as previous research has been inconsistent in the direction of intervention effects [44, 45].

If the number of missing outcomes is larger than 10% and the results of the primary outcome is significant, a worst-case scenario will be performed for the primary and secondary outcomes as sensitivity analyses. The missing outcome values in the one group will be imputed with the mean value of the primary or secondary outcome of the other group and vice versa.

The primary outcome will be tested with significance level of 5%. Analyses of the pre-defined secondary outcomes will be analyzed with no p-value adjustment due to multiplicity and the interpretation of these results will be assessed in the light of multiple testing. This means that statistically significant effects will be

interpreted in the context of increased risk of type I error. No significance testing will be performed for the exploratory outcomes.

We will apply mediation analysis to test our program theory and hypothesized assumptions of changes in specific determinants will lead to change in the primary outcome.

Process evaluation

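### With 16 schools, the primary multi-level test has no named estimator or small-sample reference and leaves out the randomisation stratum and two constrained school factors, so its true size is not fixed at 5%

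*Combined protocol and SAP*

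**What the plan says.** Under Evaluation design, Effect evaluation, 16 schools are allocated 1:1. On the stratum: "The randomization process will be stratified on whether the school was an independent general high school" or is part of a broader youth institution. On the constraint: "school size measured by number of students, proportion of parents with high educational level and degree of urbanization will be balanced".

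Under Planned statistical analysis, "Multi-level models will be used to account for the clustering of students in schools and school classes". The covariate list is explicit: "All analyses will be adjusted for sex, parental education level, parental income and baseline level of the outcome". Of the four randomisation factors only parental education appears there, and it is not described as a school-level proportion. The primary outcome is tested at 5%. The section also states that "A blinded version of the data will be used for data analysis".

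Nowhere does the document name REML or ML, a z or t reference, a degrees-of-freedom method, another small-sample correction, or a permutation test.

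**The concern.** Treatment varies only between schools, so the evidence on the contrast comes from 16 units and not from some 3,000 students. After two arm means, 14 school-level degrees of freedom remain, or 13 if baseline enters as a school mean. At that number, z and t references give visibly different p-values, as do ML and REML standard errors. A borderline primary result could be significant by one and not by another.

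A second issue acts in the other direction. Stratifying and constraining on prognostic school factors reduces the true variance of the treatment contrast. A model without those factors does not credit the reduction, so its standard error is too large and the test becomes conservative.

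The trial has one confirmatory p-value, and its error rate depends on both unstated choices.

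**Working it through.** **Inputs from the plan.** Sample size calculation: control mean 2.94, SD 2.58, ICC 0.034, 198 students per school, 30% reduction (0.30 × 2.94 = 0.882), power 0.8, alpha 0.05. Effect evaluation: 16 schools. Two-sided testing is assumed because the plan does not state sidedness; it reproduces the plan's 12 schools.

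**Plan's own figure.** Design effect = 1 + 197 × 0.034 = 7.698. A difference of 0.882 needs 135 students per arm unclustered, and 135 × 7.698 ≈ 1,040. Then 1,040 / 198 = 5.25, so 6 schools per arm and 12 in total, as stated. The student total comes to 2,080 rather than the stated 2,296; the number of schools is unaffected. The normal formula with a design effect is enough to give 12, so no few-cluster correction is visible here either.

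**Size of a Wald z-test when the omitted factors do not predict the outcome.** For balanced schools the REML statistic follows t on df = J − 2 − q, where J is the number of schools and q the number of school-level covariates.
- REML: size = 2·P(t_df > 1.96).
- ML divides the school-level residual by J, so size = 2·P(t_df > 1.96·√(df/J)).

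| Schools | df | REML z | ML z (effective cut-off) |
|---|---|---|---|
| 16, student-level baseline | 14 | 7.0% | 8.8% (1.833) |
| 16, school-mean baseline | 13 | 7.2% | 10.1% (1.767) |
| 12, school-mean baseline | 9 | 8.2% | 12.4% (1.697) |

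Fitted random-intercept models for 16 schools with no school-level covariate (8,000 null trials per setting) gave 6.8-7.3% for REML z, 8.4-9.3% for ML z, and 4.9-5.3% for t on 14 df.

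**Size under the planned allocation.** Simulation of students in classes in schools, with the plan's covariates and a school baseline mean. Assumed, because the documents do not give them:
- 7 classes of 28 per school, and class ICC 0.02;
- 4 embedded schools split 2:2;
- allocation drawn from the best 10% of the 5,544 stratum-balanced allocations;
- four factors of equal weight, explaining a share R² of between-school variance.

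There were 3,000 replicates per cell (Monte Carlo SE about 0.4 points at 5%).

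| Baseline carries the factors | R² | t, 13 df | z REML | z ML |
|---|---|---|---|---|
| not applicable | 0 | 4.7% | 6.8% | 9.8% |
| fully | 30% | 4.8% | 6.6% | 9.7% |
| fully | 60% | 3.8% | 5.7% | 8.0% |
| half | 30% | 2.9% | 4.9% | 6.6% |
| half | 60% | 2.5% | 3.9% | 5.4% |
| not at all | 30% | 3.2% | 4.8% | 7.1% |
| not at all | 60% | 1.2% | 2.2% | 3.7% |

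Adding the stratum moves the t-test to 3.5% and 2.8% (half) and to 3.8% and 1.9% (not at all). Adding all four factors gives 4.1-5.1% in all seven rows.

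A simpler school-mean simulation (stratum plus two constrained factors, no baseline covariate, best 10% or 50% of 100 sampled allocations) shows the same pattern. REML z falls from 7.3-7.4% at R² = 0 to 4.5% at 20% and 1.9-2.3% at 40%.

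**Cost of t against z.** SE = √(2 × 2.58² × 7.698 / (198 × J/2)).
- 16 schools: SE = 0.254 and 0.882/0.254 = 3.47. Power is 93% by z, and 89% by t on 12 df (school-mean baseline plus stratum).
- 12 schools: SE = 0.294 and ratio 3.00. Power is 85% by z, 76% by t on 9 df, and 75% on 8 df.
- Interval width at 12 df: 2.179/1.96 = 1.11.

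**The case against.** The tempting reading is that the primary test will run at 7-10%. The documents do not support it. The plan never chooses a z-test, and nothing in it points to ML. The allocation is also constrained: REML z is at or below 5% in four of the seven simulated rows. The 7% and 9-10% figures are the upper range, reached when the omitted factors add little beyond baseline. This part of the objection stands, and the point is limited accordingly.

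A second tempting reading is that the proposed primary model delivers exactly 5%. It does not. In those four rows the stratum-adjusted t-test runs at 3.5, 2.8, 3.8 and 1.9%, further below 5% than the REML z-test with the planned covariates (4.9, 3.9, 4.8 and 2.2%). That also stands. But z comes closer there only because two errors happen to offset each other, and the size of the offset cannot be known in advance.

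The covariate omission alone causes no inflation under a t reference, so it is the weaker half of the point. The simulations also have limits. The baseline scenarios change the residual school correlation as well (0.5, or 0 where baseline is unrelated), so they do not isolate the role of baseline. Student-level baseline was not simulated under the constraint.

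Blinded analysis data limit choosing a method by the direction of effect. They do not settle which of several p-values counts.

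**Conclusion.** The point holds as a gap in specification, not as a demonstrated inflation. The true size of the 5% primary test is not fixed by the plan. With a Wald z it could be up to about 7% (REML) or 9-10% (ML), and it falls to 5% or less (REML) if school type, size and urbanisation predict the outcome strongly beyond baseline. With a t reference it does not exceed about 5%, and it can fall to about 1-3%.

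The two omissions are read directly from the text, and the analytic rates follow from the number of schools. The lower part of the range rests on the assumed R², stratum sizes, class correlation and tightness of the constraint. The change should be made before analysis. Confidence is moderate on the magnitudes and high on the omissions.

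**What to change.** In Planned statistical analysis:

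1. Fit continuous outcomes by REML, and name either Kenward-Roger or Satterthwaite degrees of freedom. For the binary secondary outcome, use a logistic mixed model with a t reference on school-level degrees of freedom.
2. Add the randomisation stratum (school type) as a fixed effect in the primary and secondary models. State that this model gives the single primary p-value and interval.
3. Prespecify one sensitivity analysis that also adds school size, school share of highly educated parents and urbanisation. It shows whether the primary test is conservative because the constrained factors are prognostic.
4. State whether baseline and parental education enter at student or school level.

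**Cost.** This needs SAP wording and school variables already required for the randomisation. The stratum uses one school-level degree of freedom; in simulation it changes power by −1.2 to +0.7 points at 16 schools and −0.6 to +1.1 at 12, with up to 2-3 points lost at 12 in a school-mean run. The larger cost is t against z: about four points of power at 16 schools, and about nine to ten at 12, where power falls below the planned 80%. Part of z's apparent advantage comes from its liberal size. The four-factor model is kept as a sensitivity analysis because its power change against the planned t-test ranges from −4.5 to +2.4 points at 16 schools and from −14.0 to +1.1 at 12.

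Item 4 touches a separate issue, to be raised on its own. Under Data collection, "Baseline data was collected from January to March 2019, while follow-up data will be collected from March to April 2020", while the alcohol policy section places initiatives "before the new 1st year high school students begin in August 2019". Yet Outcomes defines a subgroup by the "25% lowest quantile in mean weekly alcohol consumption at baseline among students in both interventions and control group", which presumes linked students. Who the baseline respondents are must be reconciled, but it adds no weight here.

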Based on results from the Unplugged program [42], we expect a 30% lower mean number of binge drinking occasions within the last 30 days in the intervention group as compared to the control group at follow-up. Sample size calculation to estimate the number of high schools needed to recruit was performed using the

statistical software STATA v15 using *Sampsii* and *Sampclus*. The average number of binge-drinking episodes within the last 30 days was estimated based on data from the Danish National Youth Study 2014 [41]. In 2014, high school students had an average of 2.94 binge drinking occasions within the last 30 days, with a standard deviation of 2.58, an interclass correlation of 0.034, and an average of 198 enrolled 1st year students per high school (cluster size). Conventional levels of statistical power (0.8) and level of significance (0.05) were used. Under the above assumptions, calculations showed that at least 12 high schools should be recruited for the study to show a 30% reduction in the number of binge-drinking episodes within the last 30 days (6 control schools and 6 intervention school, equivalent to a total of 2,296 students). Due to the risk of loss to follow-up, we aimed at recruiting an additional 30%, corresponding to 16 high schools.

Planned statistical analysis

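### The missing-data sensitivity analysis fills each arm with a single constant and carries no imputation uncertainty, so when loss occurs within schools it is more lenient than the same shift analysed with that uncertainty

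*Combined protocol and SAP*

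**What the plan says.** The planned statistical analysis section sets one sensitivity analysis for missing data: "a worst-case scenario will be performed for the primary and secondary outcomes as sensitivity analyses". It runs only when more than 10% of outcomes are missing and the primary test is significant. The method takes one sentence: "The missing outcome values in the one group will be imputed with the mean value" found in the opposite arm, with the same done in reverse for the second arm. That gives one constant per arm per outcome, whatever the student's school, class or baseline drinking.

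For the main analysis the same section says: "Multi-level models will be used to account for the clustering of students in schools and school classes". It does not say how the filled data are then modelled or how the uncertainty of the filled values enters the standard error. That they are analysed as if observed is an inference, but no other procedure is described. No expected share of missing students is given.

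**The concern.** The check is there to show whether a significant primary result withstands missing data. A constant fill gives all missing students in an arm the same outcome and pulls every school mean in that arm towards one value. The spread between school means drives the standard error in a trial of 16 schools, so the reported precision can rise as more data go missing. The assumed shift weakens the effect as intended, but the smaller standard error gives part of that back. At stake is which significant results are called robust. The primary estimate and its test are not affected.

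**Working it through.** **Inputs.** From the sample size section: control mean 2.94, SD 2.58, intraclass correlation 0.034, 198 students per school, 30% reduction (2.94 × 0.30 = 0.882), power 0.8, significance level 0.05 (two-sided assumed). From the evaluation design section: 16 schools, 1:1, so 8 per arm. The missing share m is an assumption: 10 to 30%, equal in both arms, with 10% being the plan's own trigger.

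**The plan's own figure.** A two-sample comparison of means needs 135 per arm. The design effect is 1 + 197 × 0.034 = 7.698, giving 1,040 per arm, or 1,040/198 = 5.25 schools, rounded up to 6. This reproduces the stated 12 schools.

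**Effect of the fill.** Let D be the observed arm difference. With share m missing in each school:

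- filled school mean = (1-m) × observed school mean + m × other arm's mean
- filled arm difference = (1-2m) × D
- between-school SD, and so the standard error, = (1-m) × complete-case value
- test statistic multiplied by (1-2m)/(1-m) as written, or by (1-2m) if the standard error is kept.

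The complete-case variance of a school mean is 2.58² × [0.034 + 0.966/(198(1-m))], and the SE of the difference is √(2 × variance/8). At the planned effect:

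| m | Complete-case SE | Filled SE | Filled effect | z complete-case | z as written | z with SE kept |
|---|---|---|---|---|---|---|
| 10% | 0.256 | 0.231 | 0.706 | 3.44 | 3.06 | 2.75 |
| 20% | 0.258 | 0.207 | 0.529 | 3.41 | 2.56 | 2.05 |
| 30% | 0.261 | 0.183 | 0.353 | 3.38 | 1.93 | 1.35 |

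**Threshold at 20% missing.** On 14 degrees of freedom the critical t is 2.145. As written, the primary t must reach 2.145 × 0.8/0.6 = 2.86 (p = 0.0126). With the SE kept it must reach 2.145/0.6 = 3.57 (p = 0.0030).

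**Share of significant primary results that survive** (simulated, unadjusted school-level t test, random loss within schools):

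| m | Planned effect: as written | SE kept | Multiple imputation |
|---|---|---|---|
| 10% | 93 to 94% | 86% | 85% |
| 20% | 79% | 53% | 48% |
| 30% | 45% | 10% | 6% |

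The multiple-imputation run kept each school's own deviation but also redrew the arm means. It is therefore a little stricter than holding the shift fixed. With no true effect, survival as written against SE kept is about 60% against 36% at 10% missing, and about 26% against 6 to 7% at 20%.

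**Other loss patterns, planned effect.** With loss averaging 20% but varying between schools with an SD of about 16 points, the SE ratio is 0.86 instead of 0.80. At an SD of about 13 points it is 0.84, with survival of 74% against 52%. If one of 8 schools per arm is lost entirely and filled, the variance of school means is (6 × 0.2588 + 0.875 × 0.882²)/7 = 0.319. The filled SE is then √(2 × 0.319/8) = 0.282, against √(2 × 0.2588/7) = 0.272 for complete cases, a ratio of 1.04. For two of 8 the ratio is 1.01.

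**The case against.** Three stronger readings are tempting, and the documents support none of them.

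First, a reader might infer that the check is easier than the primary test, or could turn a null result into a positive one. It is not and essentially cannot, because (1-2m)/(1-m) is below 1. It also runs only after a significant primary result. In the simulations with even loss no non-significant primary result became significant. With no true effect and 20% missing, significance on both tests occurs in only about 1.2 to 1.3% of trials, so the survival percentages under no effect are shares of an already small group.

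Second, a reader might infer that the standard error is too small for the estimator used. In repeated sampling it is too large. The filled SE averages 0.226, 0.203 and 0.180 at 10, 20 and 30% missing, while the filled estimate varies with an SD of 0.205, 0.156 and 0.105. That is because the fill moves with the observed difference. The SE is understated only against a benchmark that holds the assumed shift fixed and lets unobserved outcomes carry uncertainty. This choice suits a stress test, since missing data should not add information, but it is a choice.

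Third, a reader might infer that the shrinkage is general. It needs loss within schools that is roughly even. The plan allows for loss to follow-up by recruiting more schools, and when whole schools are lost at the planned effect there is no shrinkage. Absence within schools remains plausible, though, because follow-up is a questionnaire answered in class and the trigger counts missing outcomes.

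It also stands that near the 10% trigger the gap is modest, and that a stricter check fails more true effects.

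**Conclusion.** The point holds in a limited form. The rule is deterministic and describes no way to carry imputation uncertainty. With roughly even loss within schools, the filled SE is about (1-m) of the complete-case SE, and the check is more lenient than the same shift with uncertainty carried. The difference is material from about 20% missing: 79% survival against 53% (48% by multiple imputation) under the planned effect. The check remains stricter than the primary test, and the primary analysis is untouched.

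The figures assume equal missing shares in both arms, a normally distributed outcome, an unadjusted school-level analysis and no class level. Covariate adjustment was not modelled, and the missing share is assumed throughout. It is worth correcting because this is the only missing-data sensitivity analysis planned and it is labelled worst-case.

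**What to change.** Keep the planned cross-arm shift but drop the constant. Multiply impute each missing outcome from the student's own-school prediction in the primary multilevel model, plus a shift equal to the observed arm difference and treated as fixed, with residual draws and standard errors combined across imputations. A simpler form reports the shifted difference with the primary-analysis SE. Either way, state in the plan how the filled data are modelled and how the standard error is obtained.

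The cost is SAP wording and a little more analysis, with no new data. The real downside is that a true effect will fail more often: at 20% missing and the planned effect, roughly 26 more of every 100 significant results would fail (79 less 53), and at 30% roughly 35 more (45 less 10). The result should therefore be presented as a stress test beside the primary result and not as a pass-or-fail condition on it.
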